12.7b) Legally Authorized Representatives (LARs) will be told that their obligation is to try to determine what the subjects would do if able to make an informed decision. If the potential subject's wishes cannot be determined, the LARs must be told they are responsible for determining what is in the subjects' best interests. LARs generally assume the same rights and responsibilities as the individuals who lack decision-making capacity in the informed consent process.

Agree Disagree

12.7c) If feasible, the investigator will explain the proposed research to the prospective research subject even when the surrogate gives consent. Although unable to provide informed consent, some persons may resist participating in a research (i.e., if they dissent) protocol approved by their representatives. Under no circumstances may a subject be forced or coerced to participate in a research study even if the LAR has provided consent.

Agree Disagree

12.7d) For subjects with fluctuating decision-making capacity or those with decreasing capacity to give consent, a re-consenting process with surrogate consent will be employed when needed

Agree Disagree

Section 12.9 HIPAA Authorization

For each category below, indicate whether or not this study involves the indicated process:

12.9a) Signed HIPAA Authorization. **New Template is available in the ? Help section**

Yes No

12.9b) HIPAA waiver to cover the entire study

Yes No

12.9c) HIPAA waiver for recruitment, screening, and/or for a portion of the study.

Yes No

12.9d) HIPAA Authorization or waiver is **not required** for some or all of the study subjects (e.g. no health data).

Yes No

Section 12.10 HIPAA Waivers and Alterations

12.10a) Describe the purpose/nature of the HIPAA waiver or alteration and list specifically, what identifiers and health information are being requested under the waiver/alteration and identify whether the waiver is for access, use, and/or collection of this information.

The purpose/nature of the HIPAA waiver is for screening activities; the study coordinator will need access to CPRS to collect and use potential subjects' names, telephone numbers, mailing address, SSNs, as well as CPRS medical records (notes) as they apply to the inclusion/exclusion criteria and the use of VASI. The following will be collected from the Veteran during the initial telephone screen.

Inclusion criteria for card-makers: (1) VASDHS Veteran with an inactive high-risk flag, (2) 18 years of age or older, (3) access to transportation to attend the group, and (4) decisional capacity. Inclusion criteria card recipients: (1) VASDHS Veteran with an active high-risk flag, (2) 18 years of age or older, and (3) decisional capacity. Exclusion criteria for card makers and recipients: (1) the absence of a mailing address, working phone number, and email address, (2) inability to read and write in English, (3) previous or current experience as either card maker or recipient, and (4) currently employed by the VA San Diego. If COVID-19 precautions are in effect, Veterans will also be screened for access to reliable computer, tablet, or smartphone with camera and internet access, as well as the willingness to participate in this study remotely. Participants' decisional capacity for informed consent in order to meet eligibility for this study will be assessed during consent (separate from screening call) via the University of California San Diego Brief Assessment of Capacity to Consent (UBACC) will be collected by the study coordinator.

12.10b) The proposed access, use, and/or disclosure of PHI involves no more than a minimal risk to the privacy of individuals.

Agree Disagree

12.10c) The plan to protect the identifiers from improper use and disclosure is adequate.

Agree Disagree

Describe the plan

To prevent improper use and disclosure of identifiers, only the PI and study coordinator will have access to the database of these identifiers, as stored it on a secure VA computer within a password protected file.

12.10d) An adequate plan to destroy the identifiers at the earliest opportunity consistent with conduct of the research, unless there is a health or research justification for retaining the identifiers or such retention is otherwise required by law.

Agree Disagree

12.10d2) Describe the plan:

The secure database with identifiers will be destroyed at the earlier opportunity, consistent with RCS-10 guidelines.

12.10e) By signing this protocol for submission, the PI is providing written assurance that the PHI will not be reused or disclosed to any other person or entity, except as required by law, for authorized oversight of the

research project, or for other research for which the use or disclosure of protected health information would be permitted by the Privacy Rule. **38 U.S.C. 7332 Information:** If the waiver of HIPAA authorization is for the use of 38 USC 7332 information (applicable to drug abuse, alcohol abuse, HIV infection, and sickle cell anemia records), by signing this protocol for submission the PI is providing written assurance that the purpose of the data is to conduct scientific research and that no personnel involved may identify, directly or indirectly, any individual patient or subject in any report of such research or otherwise disclose patient or subject identities in any manner. (Ref: 38 U.S.C. 7332(b)(2)(B))

Agree Disagree

12.10f) The research could not practicably be conducted without the waiver or alteration.

Agree Disagree

12.10f2) Describe how the waiver/alteration enables the research to be conducted

The waiver is essential is for screening subjects and having access to CPRS to collect and use the names, telephone numbers, mailing address, as well as CPRS medical records (notes) as they apply to the inclusion/exclusion criteria (see 12.10a for details on what information will be collected during the telephone screens).

12.10g) The research could not practicably be conducted without access to and use of the PHI.

Agree Disagree

12.10g2) Describe why it would be impracticable to conduct this research without the PHI described 12.10a. (v3 /8/18)

Access to and use of the PHI is critical to identifying eligible participants, sending them an introductory letter to the study, and conducting a telephone screen thereafter. The present study depends entirely on access to this PHI and could not be completed without it.

Section 13 - Alternatives to Participation

13) Describe the alternatives to participation in this research study (see ? for guidance)

The alternative to participation is to not participate. Veterans with inactive HRFs may participate in other VASDHS mental health groups; Veterans with active HRFs may continue receiving regular outreach by VASDHS' Suicide Prevention Coordinators (e.g., phone calls).

Section 14 - Potential Risks

14) Describe any potential or known risks or discomforts and assess their likelihood and seriousness (see ? for guidance)

There are minimal risks to participating in the Caring Cards group, meet-up groups (optional), or receiving cards.

Disclosure or Identification of Suicidal Ideation or Intent to Harm Self: Participants to be enrolled are at elevated risk of suicide and reporting active suicidal ideation. During structured interviews concerning suicide (via the C-SSRS and BSS) or extemporaneous discussion with rater or other staff, participants may disclose a level of risk of harming themselves that would require a higher level of care. Further, during the intervention, participants may experience an increase in suicidal ideation beyond that which they reported at baseline.

Assessments: The questionnaires are non-invasive clinical assessments associated with minimal risk. All measures are physically non-invasive, have been used in prior studies with seriously mentally ill participants, and have been found to elicit minimal distress and discomfort. Nevertheless, participation in the psychosocial evaluation and responding to questions will require time and attention. Some participants may become bored or fatigued completing the evaluation. Some participants may also become distressed during the psychiatric evaluation, which requires them to discuss their current symptoms.

Intervention Period: Risks involved in participating in this intervention are minimal. During the Baseline assessment and follow-up assessments, participants may experience feelings of anxiety or discomfort while talking about themselves and/or symptoms. Participants may also become fatigued by filling out questionnaires or answering questions in person.

In addition, card makers may experience some discomfort drawing upon their lived mental health experience to create caring cards for other Veterans in need. Card recipients may experience discomfort receiving cards, as it may remind them of their mental health concerns.

Participants do not have to answer any assessment question they do not want to, and can decide at any time to withdrawal from the study.

Confidentiality: As with any research study, a risk of disclosure of personal material exists.

COVID-19 Exposure: During the COVID-19 pandemic, all face-to-face visits (i.e., group participation and assessments) present risk for virus exposure.

Section 15 - Risk Management

15) Describe the procedures for protecting against or minimizing any potential risks/discomforts, and the adequacy of resources for conducting the study and resources participants may need as a consequence of the research. When applicable, include detail of the following safety measures: (a) The type of safety information to be collected, including AEs; (b) Frequency of safety data collection; (c) Frequency or periodicity of review of cumulative safety data; (d) Statistical tests for analyzing the safety data to determine if harm is occurring; and (e) Conditions that trigger an immediate suspension of the research. See ? for further requirements.

During the telephone screening portion of our study, risk will be mitigated by using a set of screening questions that will elicit the least amount of sensitive or personal information necessary to assess eligibility. Only qualified interviewers with significant prior experience in treatment or assessment of relevant populations/conditions will conduct these assessments. All study personnel will be trained, observed, and certified by the study's PI, who is a licensed clinical psychologist. The first three months of this study will be included focused training on assessment administration. For example, the C-SSRS has a standard series of training videos that study personnel will undergo to ensure proper administration of this instrument. Standardize trainings will take place for any instruments where this type of formal training is available.

In addition, to further mitigate risk participants will be informed that they do not have to answer any question they do not want to, and can decide, at any time, if they want to withdrawal from the study. The study PI will be available to discuss any concerns participants may have with the study.

If during the course of the study participants experience an adverse reaction during screening, assessment administration, or group participation (i.e., for card makers), imminent risk for suicide is determined, or a suicide attempt (that has not been previously recorded) is disclosed, the research team will adhere to the following to ensure Veterans' safety.

Monitoring of Suicidal Ideation: This is a challenging aspect the study and so we have developed our procedures to be consistent with the recommendations of organizations such as NIH in clinical research in people with elevated suicide risk (e.g., Issues to Consider in Intervention Research with Persons at High Risk for Suicidality). We will further refine our procedures by use of deployment focused discussions with stakeholders in the study start up phase and in collaboration with the Data Safety Monitoring board. The referral sources for this study are VASDHS' Veterans with inactive and active high-risk suicide flags. Veterans with active high-risk suicide flags are closely monitored and regularly assessed for suicide risk by the VASDHS' Suicide Prevention Coordinator (SPCs). At baseline and follow-up, participants are administered the C-SSRS and BSS. Veterans are informed during consenting that all suicidal behavior is documented in Suicide Behavior Reports in CPRS if not already entered.

As such, if any of the following items are endorsed (respective item scores are noted below) on the Beck Scale for Suicidal Ideation (BSS) a LIP will be notified immediately:

- Item 4 (2)
- Item 9 (1 or higher)
- Item 13 (2)
- Item 14 (2)

- Item 15 (2)
- Item 16 (1 or higher)
- Item 17 (1 or higher)
- Item 18 (2)
- Item 20 (1 or higher)

If any of the following items are endorsed on the C-SSRS (initial screener):

- Item 4 (Active Suicidal Ideation with Some Intent to Act, without Specific Plan)
- If a Veteran answers "Yes" to the question about preparatory acts or behaviors within the past month - i.e., "Have you taken any steps towards making a suicide attempt or preparing to kill yourself (such as collecting pills, getting a gun, giving valuables away or writing a suicide note)?"

If any of the following items are endorsed on the C-SSRS (since last contact):

- Item 4, "Have you had any intention of acting on these thoughts of killing yourself? (As opposed to you have the thoughts, but you definitely would not act on them?)"
- Item 5, "Have you started to work out, or actually worked out, the specific details of how to kill yourself and did you intend to carry out your plan?"
- Item 6 "Have you done anything, started to do anything, or prepared to do anything to end your life?"

Our safety monitoring guide details these procedures, how they are recorded, and what the staff, facility, and investigator responsibilities are. All Veterans are provided the contact information for the Veterans' Crisis Line. Any new suicidal behavior will be documented in the Suicide Behavior and Overdose Report in CPRS by research staff. Participants who elect to withdraw from the study will continue to receive suicide prevention services per VA San Diego's protocol. We will monitor these protocols during the course of the study and will make adjustments to inclusion/exclusion criteria or safety protocol in case of adverse events.

Adverse events in this research project are expected to be extremely rare. However, we have established plans for resolving any adverse event should one occur. First, during screening for the project, trained research personnel will assess (using standardized screening tools) for any serious medical or psychological conditions that may require immediate medical attention or psychiatric treatment. The rationale for this is because the presence of serious medical or psychiatric conditions would make these individuals inappropriate for the proposed research study. Should attention be required, staff will provide these individuals with information about suitable referrals, including local hospitals, clinics, and/or relevant healthcare and mental health professionals, and they will strongly encourage the individuals to follow up with these referrals.

All research personnel will complete VA TMS trainings pertinent to suicide prevention.

Confidentiality: In order to protect confidentiality, all participant data will be de-identified by assigning each participant a unique ID in computer files, and all physical files from the study will be kept in a locked cabinet in study offices at the Veterans Medical Research Foundation building in San Diego. All electronic data and files will be stored on a secure server. Only study investigators and personnel will have access to these data. All documentation will identify participants only by their Unique ID number and not other personally identifying information.

COVID-19 exposure: To mitigate participants' exposure to COVID-19, web (i.e., VVC, WebEx) or telephone-based visits may be used instead of face-to-face visits.

WebEx and DocuSign Consenting:

Veterans may feel uncomfortable using WebEx and DocuSign to sign consent forms. To mitigate this, we will offer alternative routes to obtaining signed informed consent, including the approaches in our original approved protocol (i.e., use My Health-e-Vet, using MS Azure, have Veteran send signed consent form via email, have Veterans fax, or have the study coordinator take a screen shot of the signed consent during their VVC or WebEx session).

Inclusion/exclusion criteria card makers:

With our additional exclusion criteria for card makers, we may exclude Veterans without access to reliable forms of technology. To mitigate this, we will either (1) invite Veterans to consider participating in an in-person group (if offered during study's duration), or (2) remind Veterans of alternatives to participation (i.e., other VASDHS mental health groups).

Section 17 - Potential Benefits

17) Discuss benefits that may be gained by the subject as well as potential benefits to society in general (see ? for guidance)

There is no guaranteed direct benefit to Veterans who participate in this study. This study has the potential to enhance our understanding the feasibility and acceptability of Caring Cards as a potential suicide prevention intervention, and may improve Veterans' satisfaction with VASDHS services.

Participation in CC may not directly benefit to participants. However, benefits to the individual participants may include increased social connectedness and sense of purpose. Participants' suicide risk and related behaviors may decrease. They may be more engaged in subsequent mental health appointments as well.

Section 18 - Risk/Benefit Analysis**18) Discuss why the risks to subjects are reasonable in relation to the anticipated benefits to subjects and in relation to the importance of the knowledge that may reasonably be expected to result.**

There are minimal risks to participants (e.g., Veterans may feel discomfort answering questions and/or making/receiving cards), and although there are no guaranteed direct benefits, there are potential benefits that could improve Caring Cards, as a suicide prevention intervention, as well as Veterans' satisfaction with VASDHS' services. In addition, participation may enjoy connecting with one another, receiving support from another Veteran, and doing something kind for another Veteran in need. COVID-19 exposure during face-to-face visits is another potential risk for participants. As such, web (i.e., VVC, WebEx) or telephone-based visits may be used instead of face-to-face visits.

Section 20 - Compensation for Participation**20) Provide all details and justifications of the compensation plan. See ? for detailed requirements.**

Participants will be paid a total of \$120 to complete baseline and follow-up assessments (\$60 each). We elected to provide compensation for participation due to the time commitment these assessments will require.

We would like to include two options to pay participants:

Option #1 - pay \$120 at baseline

Option #2 - pay participants at two assessment timepoints (\$60 baseline and \$60 follow-up)

Section 21 - Responsibilities and Qualifications**Here are the identified study staff members**

[name]

[name], [name], [name], [name], [name], [name], MA, LMFT, [name], [name], [name], [name], [name], [name]

21) For each staff member listed above, describe their role and qualifications. Also indicate which of the study staff are authorized to obtain consent, when applicable to the study.

[name].- P.I and clinical psychologist; will oversee management of staff, administrative tasks, database collection, publication(s), and budgetary requirements.

[name].- Non-VASDHS Collaborator and former PI; will serve as consultant to study personnel, assist with database preparation, and assist with publications.

[name].- co-I and clinical psychologist; serves as project co-investigator.

[name]. - co-I and clinical psychologist; serves as co-investigator.

[name]. - co-I and clinical psychologist; serves as co-investigator.

[name]- Will assist until permanent study coordinator is hired and added to IRB via amendment; will oversee administrative duties of the project (e.g., coordinating to secure provision of funds)

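### In Section 15 the baseline C-SSRS trigger list omits plan with intent, which the follow-up list names, and neither list states its action or is reconciled with the baseline rule in Section 9.9

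*Protocol*

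**What the plan says.** Section 15 (Risk Management, Monitoring of Suicidal Ideation) covers both assessments: "At baseline and follow-up, participants are administered the C-SSRS and BSS". It then sets out three lists.

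- **BSS.** Nine items, each with a trigger score. Immediate notification of a LIP is stated for this list.
- **Baseline C-SSRS.** The list opens "If any of the following items are endorsed on the C-SSRS (initial screener") and has two entries: "Item 4 (Active Suicidal Ideation with Some Intent to Act, without Specific Plan") and a yes to "the question about preparatory acts or behaviors within the past month".
- **Follow-up C-SSRS.** The list opens "If any of the following items are endorsed on the C-SSRS (since last contact") and has three entries: Item 4, "Have you had any intention of acting on these thoughts of killing yourself"; Item 5, on having worked out "the specific details of how to kill yourself and did you intend to carry out your plan"; and Item 6, "Have you done anything, started to do anything, or prepared to do anything to end your life".

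No action follows either C-SSRS list. Section 15 then refers to a safety monitoring guide, which is not part of the document.

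Section 9.9 (Data Safety Monitoring Board or Plan) has its own baseline C-SSRS rule. An ideation score above 2 leads to contact with the PI, a telephone evaluation, and referral to the Suicide Prevention Coordinators or emergency services as needed. Section 15 neither repeats this rule nor refers to it.

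**The concern.** Plan with intent is a trigger on the later form but is not named on the earlier one. Taken by its label, the only ideation entry in the baseline list describes intent without a specific plan. A Veteran who reports a worked-out plan with intent, but no preparatory act in the past month, then matches neither baseline entry. The same answer matches Item 5 at follow-up.

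Baseline is an awkward place for such an omission. Section 14 describes those to be enrolled as at elevated risk and reporting active suicidal ideation, so the answer is foreseeable. Section 9 provides no direct study risk assessment of recipients after each card, and their follow-up comes within one month after the last of six monthly cards. Card makers are formally assessed only at enrollment and follow-up; between these, the C-SSRS is given if a Veteran reports suicidal thoughts to the facilitator.

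An assessor who relies on the itemised list in Section 15 would have to notice the mismatch, find the other rule in Section 9.9, and decide whether the contact is a LIP or the PI.

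**Working it through.** No arithmetic beyond counting applies. The check is an entry-by-entry comparison of the two C-SSRS lists in Section 15, followed by a search of the protocol for other rules that would catch the same answer.

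**Step 1. The two lists side by side.**

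| Answer | Baseline list | Follow-up list |
|---|---|---|
| Intent | Item 4, labelled as without specific plan | Item 4, given as a question on intention |
| Plan with intent | not listed | Item 5 |
| Behaviour | preparatory acts, past month | Item 6: done, started or prepared anything |
| Action stated after the list | none | none |

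The baseline list has 1 ideation item + 1 behaviour question = 2 entries. The follow-up list has 2 ideation items + 1 behaviour item = 3 entries. The missing entry is plan with intent. The behaviour entry is also worded more widely at follow-up.

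**Step 2. Does Item 4 at baseline stand for Item 4 and above?** The wording does not say so. Four of the nine BSS entries in the same section (Items 9, 16, 17 and 20) are written as a score of 1 or higher, so the authors write a threshold where they mean one. The follow-up list also names Item 5 separately from Item 4, so it was not treated as redundant there.

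**Step 3. What action is attached?** The sentence on notifying a LIP governs the BSS list. Extending it to the C-SSRS lists is a natural inference, but it is not written.

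**Step 4. What else would catch the answer at baseline?**
- Section 9.9: PI contact for an ideation score above 2. If ideation is scored in item order, which the protocol does not print, plan with intent lies above 2 and reaches the PI.
- C-SSRS Item 4: a Veteran with a plan and intent may endorse this item as well.
- BSS: any of nine items at the same assessment.
- Section 15, general wording: a finding of imminent suicide risk, or disclosure of an attempt not previously recorded, also starts the safety procedures.

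**Step 5. When would the answer be missed?** All of the following must hold together: plan with intent, Item 4 not endorsed, no preparatory act in the past month, no BSS trigger, no finding of imminent risk, and no PI contact under Section 9.9. The protocol gives no figure for any of these, so no rate can be calculated.

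**The case against.** The strongest reply is that the protocol handles the case elsewhere. The Section 9.9 rule applies at baseline and probably reaches a plan-with-intent answer, and the BSS triggers and the imminent-risk wording apply too. This stands, and it limits the point. A reader might infer that a plan-with-intent answer at baseline goes unescalated, that escalation turns on the visit rather than the answer, or that all 80 baseline assessments are affected. The documents do not support any of these. Eighty is the number to be assessed, not the number who could fall through, and Step 5 shows how many conditions would have to coincide.

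A second reply is that the baseline list cites Item 4 by its category label, while the follow-up list cites it by its question, and that question does not exclude people with a plan. The baseline question for Item 4 is not reproduced, so a Veteran with a plan may well endorse it. This stands as a reason for caution about consequences. It does not put plan with intent on the list.

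A third reply is that the lists belong to different versions of the form: Section 27.2 says the baseline version needs an assessor and the follow-up version does not. Lists for different forms need not match word for word. The protocol does not offer this as its reason, however, and it does not explain why the answer that adds a plan to intent is absent from the baseline list.

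Finally, the safety monitoring guide may already settle the matter. It is not shown. Even if it does, the protocol's own lists should agree with it.

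**Conclusion.** The mismatch in Section 15 is real on the face of the text. Plan with intent is named in the follow-up C-SSRS list and not in the baseline list, with no reason given. Two further faults accompany it: neither C-SSRS list states its action, and Section 9.9 sets a different baseline rule with a different contact.

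The conclusion is confined to Section 15 as listed; a gap across the whole protocol is not shown. It rests on reading the baseline entry as written, without an implied threshold. The view that Section 9.9 would probably catch the answer rests on ideation scores following item order.

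This should be corrected because it concerns suicide-risk escalation and needs only wording. Confidence is medium, because the baseline form and the safety monitoring guide are not available.

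**What to change.** - Reconcile the two C-SSRS lists in Section 15 with each other and with the baseline rule in Section 9.9, so that equivalent answers are handled consistently at baseline and follow-up. If a difference is intended, state the clinical reason.
- State after each C-SSRS list what action follows and who is contacted.
- Carry the reconciled text into the safety monitoring guide.

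The responsible clinicians should decide which items and thresholds apply; none is proposed here.

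The cost is an edit to the protocol and the guide, and possibly a few more notifications at baseline. Sample size, assessment schedule and analysis are unaffected.
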